8.3.2 Fibrinogen Levels

Fibrinogen plasma level before and 1 hour after the end of each subsequent infusion and at the time of the overall clinical assessment of haemostatic efficacy.

Fibrinogen at baseline and at 1 hour after first and last infusion as well as changes of Fibrinogen from baseline will be summarized using descriptive statistics and displayed graphically.

FORMA-02	JSS Medical Research - Data Management	 <small>RESPONSIVE RELIABLE RESULTS</small>	
Statistical Analysis Plan			
Form Number: MNI-DM-BIS-01 v 6.0-T1	Current Version Number: 2.0	Previous Version Number: 1.1 9-April-2015	Date: 11-July-2016

Octafibrin will be individually dosed to achieve a recommended target fibrinogen plasma level dependent on the bleeding type (minor or major). Target level and achieved level after individually dosed as well as difference of Target level and achieved level will be summarized using descriptive statistics and displayed graphically.

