3.3 Discussion of Study Design and Choice of Control Group(s)

As there are currently no guidelines concerning fibrinogen concentrates in either the US or the EU, the study was designed following established programs for Factor IX concentrates.

Typically, the clinical evaluation of a new concentrate initially examines the IVR and the PK properties of the principal active factor. Prior to initiating the present study, comparative PK data have been obtained in study FORMA-01.

The open-label uncontrolled design and choice of study objectives are motivated by regulatory requirements for Factor IX [14] and discussions with the regulatory bodies.

The median response value used in the fibrinogen dosage calculation is the median incremental in vivo recovery reported in the interim analysis of study FORMA-01.

Although all bleeding episodes occurring throughout the study observation period will be documented, only the first bleeding episode per patient will be used for the analysis of the primary endpoint (see Section 3.1.1). This is because the study will end once the 24th enrolled patient has at least one documented bleeding episode, potentially resulting in a large diversity in the number of bleeding episodes between patients. The entirety of bleeding episodes documented in the study will be assessed as a secondary endpoint (see Section 3.1.2).

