5.4.2 Dosing for On-demand Treatment of Bleeding

For each bleeding episode that is treated as part of the study, each subject will receive at least 1 infusion of *Octafibrin* for the treatment of a major or minor acute bleeding episode on Day 1.

Octafibrin will be individually dosed to achieve a recommended target fibrinogen plasma level dependent on the bleeding type (minor or major).

- **Minor bleeding** will be treated to achieve a recommended target fibrinogen plasma level of 100 mg/dL and an accepted lower limit of 80 mg/dL.
- **Major bleeding** will be treated to achieve a recommended target fibrinogen plasma level of 150 mg/dL and an accepted lower limit of 130 mg/dL.

On subsequent study days, fibrinogen plasma levels will be measured daily to determine whether additional infusions of *Octafibrin* are needed:

- Minor bleeding will be observed for at least 3 days.
- Major bleeding will be observed for at least 7 days.

Additional Octafibrin infusions, as required

- Additional infusions of *Octafibrin* **should** be administered if the actual fibrinogen plasma level measured on subsequent study days is below the accepted lower limit of the target level (80 mg/dL for minor bleeding, 130 mg/dL for major bleeding).
- If the actual fibrinogen plasma level is above the accepted lower limit of the target level, *Octafibrin* **should not** be administered.

Definition of minor and major bleeding

- **Minor bleeding** events are defined as mild haemarthrosis or superficial muscle, soft tissue, and oral bleeding.
- **Major bleeding** events are defined as symptomatic bleeding in a critical area or organ, such as intracranial, intraspinal, intraocular, retroperitoneal, intraarticular, or pericardial bleeding, or intramuscular bleeding with compartment syndrome, or bleeding causing a decrease in haemoglobin level by 20 g/L (1.24 mmol/L) or more.

Characterisation of any other bleeding events not within these categories will be discussed individually with the investigator.

^{*}The median response in this dose calculation formula is the median incremental in vivo recovery reported in the interim analysis of study FORMA-01.

^{**}The measured level for the first infusion will be the historical level for that patient after a washout or, if below the limit of detection of the local assay, zero (0) will be used.

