9.4.3 Additional Analyses

Octafibrin use

Octafibrin will be individually dosed to achieve a recommended target fibrinogen plasma level dependent on the bleeding type (minor or major). Target level and achieved level after individual dosing as well as the difference between target level and achieved level will be summarized using descriptive statistics and displayed graphically.

The dose of the IMP used per day and in total will be summarised using descriptive statistics for minor and major bleeding events. Frequency of infusions and duration of treatment will also be summarised. The frequency of unscheduled infusions will be summarised descriptively.

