3.1.2 Secondary Objectives

- To show an association between the overall clinical assessment of haemostatic efficacy and the surrogate endpoint 'clot strength' or 'clot firmness' (referred to as 'Maximum Clot Firmness' [MCF]) that was used as a surrogate endpoint for haemostatic efficacy and determined via Thromboelastography (TEG) in the pivotal Pharmacokinetic (PK) study FORMA-01. Therefore, MCF as surrogate efficacy parameter will be determined before first infusion and 1 hour after the end of first and last infusion.
- To achieve peak target plasma fibrinogen level of 100 mg/dL in minor bleeds and 150 mg/dL for major bleeds 1 hour post-infusion.
- To determine the response to Octafibrin based on incremental in vivo recovery (IVR).
- To demonstrate the efficacy of Octafibrin in preventing bleeding during and after surgery.
- To assess the safety of Octafibrin in subjects with congenital fibrinogen deficiency, including immunogenicity, thromboembolic complications, and early signs of allergic or hypersensitivity reactions.

FORMA-02	JSS Medical Research - Data Management	 JSS <small>RESPONSIVE RELIABLE RESULTS</small>	
Statistical Analysis Plan			
Form Number: MNI-DM-BIS-01 v 6.0-T1	Current Version Number: 2.0	Previous Version Number: 1.1 9-April-2015	Date:11-July-2016

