6 GENERAL CONSIDERATIONS FOR STATISTICAL ANALYSIS

The descriptive statistics for continuous variables will be presented with number (n) of non-missing observations, mean, Standard Deviation (SD), median, minimum and maximum (or range). For categorical variables, descriptive statistics will be presented with number of eligible subjects and number (n) with percentage of observations in the various categories of the endpoint, where percentage will be based on the eligible subjects in the respective analysis set.

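### The secondary objective of reaching a 1-hour fibrinogen level of 100 or 150 mg/dL has no planned count of subjects who reach the target or the accepted lower limit.

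*SAP*

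**What the plan says.** SAP section 3.1.2 (and Protocol section 2.2) gives as a secondary objective: "To achieve peak target plasma fibrinogen level of 100 mg/dL in minor bleeds and 150 mg/dL for major bleeds 1 hour post-infusion".

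For the analysis, SAP section 8.3.2 says "Target level and achieved level after individually dosed as well as difference of Target level and achieved level will be summarized using descriptive statistics" and adds a graphical display. Protocol section 9.4.3 plans the same. SAP section 6 defines the descriptive statistics for continuous variables as n, mean, SD, median, minimum and maximum (or range). SAP sections 8.3.1 and 8.3.2 also summarise the 1-hour levels and changes from baseline, but not against target. SAP section 11 lists all data.

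Protocol section 5.4.2 sets accepted lower limits of 80 mg/dL (minor) and 130 mg/dL (major). On the dose, it says "The median response in this dose calculation formula is the median incremental in vivo recovery reported in the interim analysis of study FORMA-01", and of the level subtracted from the target, "The measured level for the first infusion will be the historical level for that patient after a washout" (zero is used if that level is below the local detection limit).

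Neither document plans a number or percentage reaching the target or the accepted lower limit, and neither says when this objective counts as met. The derived-variable table in SAP section 6.2 contains only BMI and haemostatic success. SAP section 8.3.2 does not state whether the achieved level is the local or the central laboratory value, whether the unit is the subject or the infusion, or whether this summary is split by severity.

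**The concern.** The objective is about reaching a level, so the natural question is how many subjects reached it. The planned comparison is a signed difference, and in its mean the overshoots offset the shortfalls.

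The dosing rule makes this more than a formality. Dividing by a median response aims the typical subject at the target exactly. Subjects who respond less than the median land below it, and those who respond more land above it. A mean difference close to zero is then compatible with many subjects short of target and some short of the accepted lower limit. The minimum and maximum show how far the worst case fell, but the same worst case could belong to one subject or to several.

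A count could be made later from the listings. By then the laboratory, the infusion, the unit and the threshold would all be chosen with the data in view, and SAP section 1 requires analyses not identified in the SAP to be flagged as unplanned.

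**Working it through.** The documents give no expected attainment rate or expected difference for this objective, so there is no figure of theirs to reproduce.

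**Inputs from the documents.** Target T = 100 or 150 mg/dL and accepted lower limit L = 80 or 130 mg/dL (Protocol section 5.4.2). Historical fibrinogen activity is below 50 mg/dL or below the detection limit (Protocol section 4.2), so baselines b of 0 and 40 mg/dL span most of the range. Dose = (T − b) / median FORMA-01 response.

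**Assumptions.** Neither document gives the between-subject variability of response, so a CV of 10% to 30% is assumed. Response is taken as lognormal, dosing as exact, and the true pre-infusion level as equal to the level used in the formula.

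**Model.** Let R be the subject's response divided by the median used for dosing, with median m (m = 1 if the FORMA-01 median carries over) and s = √ln(1 + CV²).

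- Achieved level = b + (T − b) × R
- P(below target) = Φ(−ln m / s)
- P(below lower limit), m = 1: Φ(ln[(L − b)/(T − b)] / s)
- Mean of target minus achieved, m = 1: (T − b) × (1 − √(1 + CV²))
- SD of the difference, m = 1: (T − b) × CV × √(1 + CV²)

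**If the median carries over (m = 1).** Φ(0) = 50% are below target at any CV and any baseline, and the median difference is 0. For the lower limit, with s = 0.0998 at CV 10% and 0.2936 at CV 30%:

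| Bleed, baseline | (L − b)/(T − b) | Below lower limit, CV 10% to 30% | Mean difference (mg/dL) | SD (mg/dL) |
|---|---|---|---|---|
| Minor, 0 | 0.800 | 1% to 22% | −0.5 to −4.4 | 10 to 31 |
| Minor, 40 | 0.667 | 0% to 8% | −0.3 to −2.6 | 6 to 19 |
| Major, 0 | 0.867 | 8% to 31% | −0.7 to −6.6 | 15 to 47 |
| Major, 40 | 0.818 | 2% to 25% | −0.5 to −4.8 | 11 to 35 |

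Example: minor, baseline 0, CV 30%: ln(0.8)/0.2936 = −0.760, and Φ(−0.760) = 22%.

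**If the median does not carry over (CV 20%, s = 0.198, baseline 0).**

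- m = 0.9: Φ(0.532) = 70% below target. Mean difference 100 × (1 − 0.9 × 1.0198) = +8 mg/dL (minor), and +12 for major.
- m = 1.1: Φ(−0.481) = 32% below target. Mean difference −12 mg/dL (minor) and −18 (major).

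**What the planned summary would look like.** For 24 minor-bleed subjects at m = 1, CV 20% and baseline 0, simulation gives a mean difference of about −1.9 mg/dL (95% range −10.3 to 5.9), an SD of about 20, and a largest shortfall of about 31 mg/dL (19 to 46). Twelve subjects are short of target (7 to 17). The SD and range make the spread plain, but no planned statistic gives the count.

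**The case against.** The strongest reply is that the plan already reveals most of this. A reader might infer that the objective is judged by the average difference alone. The documents do not support that: SAP section 6 adds SD, median, minimum and maximum, section 8.3.2 adds graphs, and section 11 adds listings. Only in the mean do overshoots and shortfalls cancel. A median difference of zero itself tells a careful reader that about half were short of target. SAP section 8.3.3 also tabulates incremental recovery by infusion day and severity. This stands. What remains missing is a stated proportion, above all for the accepted lower limit, which none of these statistics supplies.

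A reader might also infer that half the subjects fall short by design. That needs the trial's median response to match the FORMA-01 interim value, which neither document gives. A trial median 10% lower would show up in the planned mean. This also stands, but the absence of a count does not depend on it.

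It can further be said that the listed endpoint is the continuous fibrinogen level, that the target is described as recommended with an accepted lower limit, and that nothing in the plan says a mean near target meets the objective. Those points are fair. They argue for reporting both thresholds, so that a level just under target is not presented as a plain miss. They do not argue for reporting neither.

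Finally, intervals will be wide. With 12 of 24, the exact 95% limits (Beta quantiles with parameters 12, 13 and 13, 12) are 29% and 71%, and severity strata will be smaller. That is a real limit on precision, and it is better shown than left unstated.

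**Conclusion.** The point holds as a gap in the analysis of a secondary objective. Comparison with target is limited to descriptive summaries and graphs of target, achieved level and their difference. No proportion reaching the target or the accepted lower limit is planned. This follows from the text and needs no assumption.

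The size is conditional. About half below target with a mean difference near zero requires the FORMA-01 median to carry over. A trial median of 0.9 or 1.1 times that value gives about 70% or 32% below target (CV 20%, baseline 0), and the mean moves with it. Against the accepted lower limit, an assumed CV of 10% to 30% gives about 1–22% (minor) and 8–31% (major) at baseline 0, and 0–8% and 2–25% at baseline 40 mg/dL. For minor bleeds the range starts at essentially none, so a sizeable shortfall is possible but not established.

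It would go too far to say that the plan conceals shortfalls or leaves the objective unexamined. It examines the objective descriptively, without the count that the objective calls for. This is an inexpensive improvement worth making, and it does not touch the primary analysis.

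**What to change.** In SAP section 8.3.2, pre-specify as the main analysis of this objective, for the first infusion of each subject's first bleed, the number and percentage of subjects whose 1-hour central-laboratory Clauss level is (a) at or above the target and (b) at or above the accepted lower limit. Present this separately for minor and major bleeds, with exact 95% CIs. State how subjects without a 1-hour sample enter the denominator. Keep the target, achieved and difference summaries and graphs as support.

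Naming the laboratory, infusion and unit in advance also settles what the achieved level means in that section.

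The cost is one extra table from data already collected. The downside is wide intervals in small severity strata and a figure that may look less favourable than a mean difference. No change to dosing is implied.

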8.3.3 In-Vivo Recovery

- Calculation and analysis of IVR will be performed for the Clauss method only.
- Response (incremental IVR) will be calculated as the maximum increase in plasma fibrinogen (i.e., Clauss data) as compared to pre-infusion, within the 12 hours (will usually refer either to the 60 minutes or the 3 hours after the first and the last infusion and refer to the 60 minutes time point after the other infusions) following infusion (expressed as absolute concentration in plasma [mg/dL]), divided by the exact dose of Octafibrin (expressed as mg/kg dosed).
- Incremental IVR (response) (mg/dL increase/ [mg/kg b.w.]) = Maximum increase in fibrinogen plasma level within 12 hours compared to pre-infusion (mg/dL) / (exact dose of component in IMP administered [mg]/b.w. [kg]).

Classical IVR will be calculated as the maximum increase in plasma fibrinogen (i.e., Clauss data) as compared to pre-infusion, within 12 hours (will usually refer either to the 60 minutes or the 3 hours after the first and the last infusion and refer to the 60 minutes time point after the other infusions) following infusion (expressed as absolute concentration in plasma [mg/dL]), divided by the total dose of Octafibrin per expected plasma volume (expressed as mg/dL, expected plasma volume being estimated based on the blood volume formula described by Nadler).

Classical IVR (%) =

$$100\% \times \frac{\text{actual/expected increase}}{\text{maximum increase in fibrinogen plasma level within 12 hours compared to pre-infusion (mg/dL) } \times \text{plasma volume (dL)} / (\text{exact dose of component in IMP administered [mg]})}$$

$$\text{IVR} \left| \frac{(\text{IU} / \text{dL})}{(\text{IU} / \text{kg})} \right| = \frac{\Delta \text{ value} \left| \frac{\text{IU}}{\text{dL}} \right|}{\text{dose (IU)} / \text{body weight (kg)}}$$

Response and classical IVR will be calculated for each infusion of each subject. Descriptive tables will show the distributions of the 2 parameters per infusion day separated for minor and major bleeding. An exploratory analysis using a repeated-measures analysis of covariance model will analyze whether the response/classical IVR changed over time. The dose (mg/kg) associated with the respective IVR will be held as covariate in the model. The response/IVR over time and dose will also be presented in scatter plots for all subjects and by major/minor bleeding.

FORMA-02	JSS Medical Research - Data Management		
Statistical Analysis Plan			
Form Number: MNI-DM-BIS-01 v 6.0-T1	Current Version Number: 2.0	Previous Version Number: 1.1 9-April-2015	Date: 11-July-2016

8.3.4 Efficacy of Octafibrin in All Bleeding Episodes

The efficacy of Octafibrin in the treatment of all bleeding episodes recorded throughout the study observation period will be assessed in the same way as the efficacy of Octafibrin in the treatment of the first bleeding episode per patient (see Section 9.4.1).

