6.1.2.5 Day 30 (29 Days after the First Infusion)—Final Examination

On Day 30 (± 1 week), the following assessments will be performed:

- Physical examination.
- Blood draw for:
 - immunogenicity
 - retention plasma samples for potential retesting.
- AEs and concomitant medications.

The Day 30 assessment concludes the series of observations by bleeding episode. No further study-related assessments will be performed, unless safety concerns (e.g., ongoing AEs) require follow-up.

Subjects returning to the study site for another acute bleeding episode within the study observation period will again undergo the same Day 1 to Day 30 assessments as outlined in Section 6.1.2.1 through Section 6.1.2.5. At the end of the study duration, all subjects will be asked to return for a Study Completion Visit as summarised in Section 6.1.4.

If a patient experiences another bleeding event between Day 14 and Day 30, this will be treated as a new bleeding event, provided that it is not directly related to the prior event. In this case, the Day 30 evaluations will be postponed until 30 days after the start of the new bleeding episode.

Any additional bleeding episodes will be documented in the same way as the first bleeding episode. These will not be used for the analysis of the primary endpoint, but they will be analysed as a secondary endpoint.

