3.2.2 Secondary Endpoints

The secondary efficacy endpoints are:

- MCF assessment before first infusion and 1 hour after end of first and last infusion of each documented bleeding episode.
- Fibrinogen plasma level before and 1 hour after the end of each infusion as well as at the time of the overall clinical assessment of haemostatic efficacy (i.e., 24 hours after the last infusion of each documented bleeding episode).
- Response as indicated by incremental IVR, calculated as the maximum increase in plasma fibrinogen (Clauss data) between pre-infusion and 1 and 3 hours post-infusion.
- Efficacy of Octafibrin in all bleeding episodes collected in the study using the investigator's overall clinical assessment of haemostatic efficacy for bleeding based on a 4-point haemostatic efficacy scale.

Efficacy of Octafibrin in surgical prophylaxis will be assessed at the end of surgery by the surgeon and post-operatively by the hematologist using the following scales:

Category	Definition
Intra-operative efficacy as assessed by surgeon (at the end of the surgery = after last suture)	
Excellent	Intra-operative blood loss* was lower than or equal to the average expected blood loss for the type of procedure performed in a subject with normal haemostasis and of the same sex, age, and stature.
Good	Intra-operative blood loss* was higher than average expected blood loss but lower or equal to the maximal expected blood loss for the type of procedure in a subject with normal haemostasis.
Moderate	Intra-operative blood loss* was higher than maximal expected blood loss for the type of procedure performed in a subject with normal haemostasis, but haemostasis was controlled.
None	Haemostasis was uncontrolled necessitating a change in clotting factor replacement regimen.

*All excludes unexpected blood loss due to surgical complications, i.e.,

- Direct injury of a vessel (artery or vein)
- Vessel injury not adequately responding to routine surgical procedures achieving haemostasis
- Accidental injury of parenchymatous tissue (e.g., liver, lung)

FORMA-02	JSS Medical Research - Data Management	 RESPONSIVE RELIABLE RESULTS
Statistical Analysis Plan		
Form Number: MNI-DM-BIS-01 v 6.0-T1	Current Version Number: 2.0	Previous Version Number: 1.1 9-April-2015
Date:11-July-2016		

Post-operative efficacy as assessed by haematologist

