4.3 Study Duration

4.3.1 Planned Duration for an Individual Subject

For subjects receiving on-demand treatment.

- the individual **subject observation and follow-up period** for each documented episode starts with the first dose of Octafibrin administered for on-demand treatment of an acute bleeding episode (Day 1) and will be followed for up to Day 30.
- Each subject's **treatment observation period** is defined according to the severity of the event and will last at least 3 days for minor and 7 days for major bleeding episodes.

For subjects undergoing surgical prophylaxis.

- the **surgical observation period** starts with the first dose of Octafibrin administered prior to elective surgery (Day 1) and, depending on the severity of the event, will last at least 3 post-operative days for minor and 7 post-operative days for major surgeries or until the day of the last post-operative infusion, whichever comes last.

During the study observation period, enrolled patients will be treated for any bleeding episodes or planned surgeries that can be managed under the protocol. Patients may remain in the study until the 24th patient has at least one documented bleeding episode.

As many bleeding episodes or surgeries as possible occurring throughout the study observation period will be documented. Only the first bleeding episodes will be used for the analysis of the primary endpoint (see Section 3.2.1). All bleeding episodes documented in the study will be assessed as a secondary endpoint (see Section 3.2.2).

Patients who were screened for the study but do not present with a bleeding episode or planned surgery during the study observation period will be considered 'no treatment' patients.

The individual observation period by subject starts with the first dose of Octafibrin administered for on-demand treatment of an acute bleeding episode or prior to elective surgery (Day 1). Subjects enrolled will be treated for any bleeding episodes or planned surgeries during the study observation period. They may remain in the study until the 24th subject has at least one documented bleeding episode.

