8 EFFICACY ANALYSIS

8.1 Primary Efficacy Analysis

For bleeding efficacy, the primary endpoint is the overall clinical assessment of the haemostatic efficacy of Octafibrin in treating the first documented bleeding episode of each patient.

The first bleeding episode covers the time period from the first Octafibrin infusion until 24 hours (i.e., 1 day) after the last infusion or the end of the treatment observation period, whichever comes last. Frequency distribution will be provided for the haemostatic efficacy scale data. In addition, a 95% CI for the success rate in haemostatic efficacy (excellent or good) according to Casella (Blyth-Still-Casella interval) will be computed using StatXact® software.

For the following subjects the haemostatic efficacy outcome will be set to the worst category i.e., "none":

- Subjects who withdraw from the study due to lack of efficacy.
- Subjects receiving cryoprecipitate, or concentrates containing fibrinogen other than the IMP between first infusion and efficacy assessment (unless it is clearly documented that these products were administered for reasons unrelated to efficacy [e.g., pharmacy error]).
- Subjects with missing haemostatic efficacy assessment.

Haemostatic efficacy will be displayed by co variables (sex, age groups, race, weight and type of bleeding) in tables or with co variables in listings depending on the number per subgroup.

FORMA-02	JSS Medical Research - Data Management		
Statistical Analysis Plan			
Form Number: MNI-DM-BIS-01 v 6.0-T1	Current Version Number: 2.0	Previous Version Number: 1.1 9-April-2015	Date: 11-July-2016

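### SAP 8.3.4 applies the one-bleed-per-patient binomial interval to all bleeds with no rule for repeat bleeds in the same patient, so the interval may be too narrow

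*SAP*

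**What the plan says.** SAP 3.2.2 lists as a secondary endpoint "Efficacy of Octafibrin in all bleeding episodes collected in the study". SAP 8.3.4 gives its analysis in one sentence: it "will be assessed in the same way as the efficacy of Octafibrin in the treatment of the first bleeding episode per patient". The sentence refers the reader to a Section 9.4.1, which the SAP does not contain. Protocol 9.4.1 is the primary analysis, and its counterpart in the SAP is 8.1. There the analysis is a frequency table of the four-point scale, and in addition "a 95% CI for the success rate in haemostatic efficacy (excellent or good) according to Casella (Blyth-Still-Casella interval) will be computed". Protocol 9.4.2.3 has the matching sentence for all bleeds.

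The number of bleeds per patient is not capped. SAP 4.3.1 states: "As many bleeding episodes or surgeries as possible occurring throughout the study observation period will be documented". Protocol 6.1.2.5 confirms that repeat bleeds re-enter the full cycle: "Subjects returning to the study site for another acute bleeding episode within the study observation period will again undergo the same" assessments. The study may run for up to five years (SAP 4.3.2). Protocol 3.3 expects that bleed counts could differ widely between patients, and for that reason limits the primary analysis to first bleeds.

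Elsewhere the SAP does deal with repeated data or limits its claims. For recovery, SAP 8.3.3 says: "An exploratory analysis using a repeated-measures analysis of covariance model will analyze whether the response/classical IVR changed over time". For surgery, SAP 8.3.5 describes the evaluation as descriptive. SAP 8.3.4 has neither a correlation rule nor a descriptive-only label.

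**The concern.** A binomial interval assumes independent outcomes. If one patient's bleeds tend to respond alike, each further bleed from that patient adds less information than a bleed from a new patient. The interval then overstates how precisely the all-bleeds success rate is known, and a few frequent bleeders can drive the estimate. SAP 1 says that the planned analyses go into regulatory submissions, so the interval would be read outside the trial team.

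Three smaller wording gaps come with it:

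- (a) The cross-reference is stale. Protocol 9.4.1 (version 6.0) has a 90% interval and SAP 8.1 a 95% one. SAP 1 says that the SAP replaces the protocol's statistical sections, so 95% governs.
- (b) An episode denominator is the natural reading of SAP 3.2.2 but is not stated. The general rule in SAP 6 is worded per subject: "where percentage will be based on the eligible subjects in the respective analysis set".
- (c) SAP 8.1 sets the outcome to the worst category in three situations. Two attach to a particular assessment. The third, "Subjects who withdraw from the study due to lack of efficacy", does not say which of a patient's several episodes it affects.

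**Working it through.** **Reproducing the plan's figure.** SAP Table 1 gives, for one bleed in each of 24 patients at a true rate of 0.95, a probability of 0.994 of at least 20 successes, and an interval of 0.633–0.941 for 20/24. Recalculation gives 0.994 and 0.634–0.941. The intervals for 19, 21 and 22 successes also agree to within 0.001, so the interval code can be trusted.

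**Inputs.** From the documents: 24 patients, a 95% two-sided Blyth-Still-Casella interval, and true success of 0.95 (SAP 8.2) or 0.90 (Protocol 9.1). Assumed, because the documents give neither: ICC of 0.1, 0.2 or 0.4, and four patterns of bleed counts:

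- 2 bleeds each (48 in total)
- 48 uneven: 10, 6, 4, 3, 3, 2, 2, 2, and 16 patients with 1
- 4 bleeds each (96 in total)
- 89 uneven: 14, 12, 10, 8, 6, 5, 4, 4, 3, 3, 3, 2, 2, 2, 2, and 9 patients with 1

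**Design effect.** With m bleeds per patient, DEFF = 1 + (Σm²/Σm − 1) × ICC. At ICC 0.2:

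- 2 each: 1 + (96/48 − 1) × 0.2 = 1.20
- 48 uneven: 1 + (198/48 − 1) × 0.2 = 1.63
- 4 each: 1 + (384/96 − 1) × 0.2 = 1.60
- 89 uneven: 1 + (649/89 − 1) × 0.2 = 2.26, so the effective number of bleeds is 89/2.26 ≈ 39.4

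**Coverage of the planned interval.** Beta-binomial simulation, 20,000 trials per scenario, counts unrelated to outcome. Entries are percentages at ICC 0.1 / 0.2 / 0.4.

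| Pattern | Coverage, success 0.95 | Lower limit above truth, 0.95 | Coverage, success 0.90 | Lower limit above truth, 0.90 |
|---|---|---|---|---|
| 2 each | 96.1 / 95.3 / 94.2 | 0 / 0 / 0 | 96.9 / 96.1 / 94.0 | 0.7 / 1.0 / 1.9 |
| 48 uneven | 94.6 / 92.8 / 90.7 | 0 / 0 / 0 | 95.3 / 92.7 / 88.7 | 1.1 / 1.8 / 2.9 |
| 4 each | 94.7 / 92.2 / 86.2 | 1.5 / 2.4 / 5.5 | 92.1 / 88.5 / 82.0 | 5.1 / 7.3 / 11.4 |
| 89 uneven | 89.7 / 85.0 / 76.5 | 2.7 / 4.5 / 9.2 | 88.4 / 82.2 / 71.4 | 4.7 / 7.8 / 13.6 |

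The nominal values are 95% for coverage and 2.5% for the lower limit. Under independence, coverage is 95.3–97.5%.

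**A different uneven pattern.** With 96 bleeds (12 patients with 1, 6 with 3, 4 with 8, one with 14, one with 20), true rate 0.90 and an unadjusted Clopper-Pearson interval, coverage is 90.3 / 77.6 / 67.2% at ICC 0.1 / 0.3 / 0.5. The result does not hang on one set of counts.

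**What it does to a reported interval.** Take 85 successes in the 89 uneven bleeds (95.5%):

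- planned interval: 89.4–98.5%, 9.1 points wide
- Clopper-Pearson, unadjusted: 88.9–98.8%, 9.9 points
- Clopper-Pearson on the effective n of 39.4: 83.7–99.6%, 15.9 points

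Of the 15.9 − 9.1 = 6.8 points of widening, 0.8 comes from changing the method and 6.0 from the design effect.

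**Does the adjusted interval work?** With the ICC fixed at 0.2 in the formula and a true ICC of 0.1, 0.2 or 0.4, Clopper-Pearson on n/DEFF covers 93.6–99.3% over all four patterns and both success rates. Its lower limit is above the truth in at most 3.2% of trials. Clopper-Pearson without the adjustment does not solve the problem: 92.6 / 88.3 / 79.8% for 89 uneven bleeds at 0.95.

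**The case against.** The strongest case is that little rests on this interval.

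- **Direction of error.** At the SAP's own planning rate of 0.95, the lower limit exceeds the truth in these patterns only when every bleed succeeds. It is then 0.960 (89/89) or 0.963 (96/96), which is 1.0–1.3 points too high. With 48 bleeds it never happens, since 48/48 gives 0.934. All other misses understate efficacy. The larger errors need a rate of 0.90, which comes from protocol version 6.0. This stands for 0.95, but 0.95 is a planning assumption, and the true rate could be lower.
- **The documents protect the confirmatory claim.** The test in SAP 8.2 concerns the proportion of patients, and Protocol 3.3 limits it to first bleeds because counts may be uneven. This stands, and it limits the severity. It does not help the all-bleeds analysis, where nothing addresses the same unevenness.
- **SAP 8.3.4 names no interval.** True: carrying it over is an inference. But both SAP 8.1 and the protocol section that the stale reference points to include one, so a programmer following the text would compute it.
- **The ICC and bleed counts are assumed.** True. The missing rule is certain; the size of its effect is not.
- **The comparison with recovery is loose.** The model in SAP 8.3.3 is an exploratory look at change over time in a continuous measure. It shows that repeated data were considered there. It does not establish a clustering policy for the whole SAP.

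**Conclusion.** The concern holds as a conditional one. Read as written, the SAP gives all bleeds an interval that is valid only if bleeds within a patient are independent, and it says nothing about what to do if they are not. The loss is negligible with two evenly spread bleeds per patient. It becomes material with about four bleeds per patient at the higher ICCs, or with many bleeds in few patients, where coverage of the nominal 95% interval falls to between 71.4% and 89.7% in the 89-bleed pattern. These figures rest on assumed ICCs and counts and on counts being unrelated to outcome.

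This is worth fixing before the analysis but does not threaten the trial's main conclusion: the endpoint is secondary, has no threshold test, and leaves the primary analysis untouched. The three wording gaps alone would be clerical. Protocol version 7.0, on which the SAP is based, was not available for this check.

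**What to change.** Rewrite SAP 8.3.4 as follows:

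1. Refer to SAP 8.1 and its 95% level. Define the denominator as treated, documented episodes. Apply the worst-category rules episode by episode, and say which episodes are affected when a patient withdraws for lack of efficacy.
2. Report the episode-level success rate descriptively without an interval, or with one that allows for within-patient correlation. One option is an exact interval on n/DEFF, with a prespecified ICC labelled as an assumption and a sensitivity range such as 0.1–0.4.
3. Report the number of bleeds per patient and a summary that weights each patient equally.

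Percentile cluster bootstrap and ratio-estimator intervals need caution, not a ban. They have zero width when every episode succeeds, which happens in 1.5–17.9% of trials at success 0.95 and at most 2.9% at 0.90 (ICC 0.1–0.4). At 0.95 they cover less than the planned interval, though for 89 uneven bleeds at ICC 0.4 the gap is marginal (ratio 76.3%, bootstrap 75.6%, planned 76.5%). At 0.90 with 89 uneven bleeds they do better than the planned interval but stay below nominal (at ICC 0.2: ratio 86.4%, bootstrap 87.9%, planned 82.2%).

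The cost is one SAP paragraph and a few lines of code. The descriptive option needs no ICC. The n/DEFF option depends on an ICC for which the documents have no source. It is conservative if bleeds are independent (98.7–100% coverage with the ICC set to 0.2), and it is wider: for 89 uneven bleeds at success 0.95 and ICC 0.2 the mean width is 15.9 points, against 9.1 for the planned interval.
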